This arm will be compared to the SGLT2 inhibitor standard of care arm. Patients eligible for SGLT2 inhibitor will be randomized to either an SGLT2 inhibitor or no SGLT2 inhibitor. These same patients may be randomized to other therapies within this master protocol. The comparison will be between those randomized to SGLT2 inhibitor vs those randomized to no SGLT2 inhibitor.

The primary Bayesian statistical model (see Statistical Analysis Plan) will be used for modeling the effect of SGLT2 inhibitor in comparison to no SGLT2 inhibitor with the following exceptions:

1. The model will contain a main effect for each other therapy that was randomized for each patient.
2. Site will not be included in the primary analysis model, but instead the country for the site will be included.

The Statistical Analysis Plan presents the interim analysis schedule and adaptive decision rules.

The primary analysis for SGLT2 inhibitor will be restricted to only patients in the intent-to-treat for SGLT2 inhibitor. This group are those patients that have been randomized to potentially receive an SGLT2 inhibitor. No patients that were not randomized to yes/no for SGLT2 inhibitor will be used in the primary analysis for SGLT2 inhibitor.

A10.12 Safety Reporting

Safety reporting will be the same as outlined in the Master Protocol. In addition, serious adverse events of DKA will be collected.

A10.13 References

2. McMurray JJV, Solomon SD, Inzucchi SE, Køber L, Kosiborod MN, Martinez FA, Ponikowski P, Sabatine MS, Anand IS, Bělohlávek J, Böhm M, Chiang CE, Chopra VK, de

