7.1.1 Visit 1 and Hospitalization Visits (see arm-specific appendices for details)

Visit 1 (Screening and Randomization)

1. Informed consent obtained
2. Assessment of inclusion/exclusion criteria assessed
3. Screening, consisting of reviewing participant medical history and information in their chart such as height, weight, vital signs, and normal clinically performed laboratory assessments, including pregnancy test for all women of childbearing age.
4. If confirmed eligible, following randomization, initiation of treatment with the assigned strategy

Hospitalization Visits

1. Recording of specifics of study treatment and adherence according to assigned arm
2. Laboratory assessments as part of standard of care
3. Daily WHO ordinal assessment
4. Ongoing daily outcomes and safety assessment

7.1.2 28 days and/or Date of Hospital Discharge

1. Recording of outcomes and safety assessments as reported by participant or observed by investigator
2. WHO Ordinal Assessment
3. Recording of vital status and ascertainment of events
4. Recording of participant's adherence to treatment strategy, if patient is in hospital

These assessments will be ascertained at discharge, or at 28 days, whichever comes first. Participants must be followed for vital status until discharged from the hospital or another care facility (if transferred on organ support) up to 90 days.

7.1.3 90 days post-randomization

1. Recording of vital status
2. May include quality of life and functional status assessment

3. May include recording of hospital readmissions

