Sexually active women of childbearing potential must use highly effective form(s) of birth control (contraception) until the treatment with an SGLT2 inhibitor has been completed. If a participant reports being pregnant during the 28 day treatment period the SGLT2 inhibitor will be permanently discontinued.

A10.5 Duration of treatment

Treatment with dapagliflozin (or empagliflozin/another SGLT2 inhibitor) will be continued through Day 28.

A10.6 Discontinuation of study intervention

At any time, patients are free to discontinue treatment or withdraw from the study, without prejudice to further treatment. A patient that decides to discontinue treatment will always be asked about the reason(s).

Discontinuation from investigational product is not the same as complete withdrawal from the study. It is essential to collect data for all patients throughout the study. For that reason, a patient who discontinues treatment should optimally continue to follow up study assessments up to and including day of discharge (or Day 28). Alternatively, if the patient does not agree to this approach, modified follow-up should be arranged (eg, less frequent assessments, one contact at Day 30, or other means). Patients who agree to some kind of modified follow up are still participating in the study.

If a patient for some reason cannot be reached during the study, every attempt should be made to retrieve as much information regarding this patient as possible. The site should continuously try to reach the patient, the patient's family, or pre-identified contact person and search for information regarding the patient's status in applicable sources to protect the validity of data. These attempts should be documented.

A10.7 Study Schedule

Activity	Screening/ Enrollment	Hospital Duration	28 days or hospital discharge ⁺	90 days post randomization and long term follow-up ⁺⁺
Eligibility				
Consent	X			
Demographic and Medical History	X			
Assessment of Inclusion/Exclusion criteria	X			
Self-reported race/ethnicity and sex	X			
Pregnancy Test, for women of childbearing potential	X			
Study Drug Administration				
Randomization	X			
Study treatment	X	X	X	
Study Procedures				
Height	X			
Weight	X			
Vital signs	X	X		
Concomitant medications	X	X		
WHO ordinal assessment	X	X	X	X
Quality of Life and Functional Status [#]	X			X
Outcomes assessment		X	X	X
SOC Laboratory Assessments				
Chemistry panel	X	X	X [^]	
CBC with platelet count	X	X	X	
Blood Group [*]	X			
PT, PTT if known	X	X		

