D-dimer ^{***}	X	X	X	
Troponin ^{****}	X	X	X	
Coagulation and inflammatory markers ^{*****}	X	X	X	
Optional Biorepository	X	X		
BNP or NT-proBNP ^{*****}	X	X	X	

[^]Chemistry panel (e.g. creatinine, acid-base) is strongly recommended to be measured at days 1,3,7,14, and at hospital discharge. Monitoring of acid-base balance in patients with T2DM during hospitalization represents a standard of care in most institutions; if there is a clinical concern for DKA due to acid base status, this should be further investigated (see A10.8.1).

^{*}Blood group taken from hospital record or self-report if that is not available.

^{**} Frequency and mode (Anti-factor Xa/PTT) of testing will be based on site routine. Anti-factor Xa monitoring is preferred over PTT

^{***} Baseline D-dimer is recommended. All values collected should be recorded.

^{****}Strongly recommended as part of routine care, all values collected should be recorded

^{*****}Optional, listed in case report form

[#]Participants may be assessed for functional status and quality of life that reflects baseline status pre-COVID illness and functional status and quality of life at 90 days when contacted to ascertain vital status. (Instruments detailed in the manual of operations).

⁺Assessments indicated in the table above will be ascertained at discharge or 28 days, whichever comes first. Participants must be followed for vital status until discharged from the hospital or another care facility (if transferred on organ support) for up to 90 days. To maximize retention, participants will be contacted intermittently post-discharge, and that contact will be recorded in the EDC. For participants discharged prior to Day 28, this will include information about treatment adherence, to be collected as close to 30 days post-randomization as possible.

⁺⁺Participants will be contacted to ascertain vital status.

A10.8 Potential Risks & Benefits

A10.8.1 Known and Potential Risks

The standard of care plus SGLT2 inhibitor group may receive anticoagulants and/or antiplatelet or additional antithrombotic therapies agents as part of standard care. SGLT2 inhibitors are not known to have any impact on bleeding or thrombosis.

The safety profiles of dapagliflozin (and empagliflozin) are already well established from prior clinical studies in various clinical settings. These studies have demonstrated that SGLT2 inhibitors are generally safe and well tolerated.

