- Ketonemia ≥ 3.0 mmol/L and/or significant ketonuria (more than 2+ on standard urine sticks) in the absence of elevated lactate (lactate should be <2 mmol/L to be considered a potential DKA) and
- At least one of the following criteria suggesting high anion gap metabolic acidosis:
 - (a) Arterial or Venous pH ≤ 7.3
 - (b) Serum bicarbonate ≤ 18 mEq/L
 - (c) Anion gap $[\text{Na} - (\text{Cl} + \text{HCO}_3)] > 10$

If a diagnosis of DKA is confirmed, treatment with SGLT2 inhibitors should be permanently discontinued.

A10.8.2 Known Potential Benefits

Preliminary data from DARE-19 trial strongly suggest that use of SGLT2 inhibitors in patients hospitalized with Covid-19 may reduce the risk of organ failure or death from any cause via a number of pathophysiologic pathways, including favorable effects on endothelial function, oxidative stress, inflammation, oxygen-carrying capacity and tissue hypoxia, as well as through inhibition of glycolysis and lipogenesis.

This arm seeks to test the hypothesis that the SGLT2 inhibitors dapagliflozin or empagliflozin, on top of standard of care therapy, would decrease adverse events, including death and organ support free days. This trial will contribute to the body of generalizable knowledge about SGLT2 inhibitor therapy and the role of organ protection through SGLT2 inhibition in Covid-19 disease to minimize the risk of adverse events in patients hospitalized with Covid-19.

All patients in the study are expected to be treated optimally according to background local standard of care therapy, including treatments to control co-morbidities. SGLT2 inhibitors dapagliflozin or empagliflozin will be administered in addition to these treatments. These patients are hospitalized and will receive close medical attention, irrespective of treatment allocation.

A10.9 Event Adjudication

A subset of thrombotic events will be centrally adjudicated, with the proportion adjusted as needed based on agreement between the site and the event committee.

A10.10 Safety Analyses

The rate of SAEs (including DKA) will be monitored. The DSMB will review the number of events, the event rates, and the posterior mean and 95% credible intervals for the event rates, difference between arms, and odds-ratios between arms will be summarized.

A10.11 Statistical Analyses

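### Arm F dosing continues to day 28 after discharge, but the plan does not define how ketoacidosis, other SAEs or readmission are ascertained during dosing at home

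*Protocol*

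**What the plan says.** A10.5 sets the length of treatment in Arm F: "Treatment with dapagliflozin (or empagliflozin/another SGLT2 inhibitor) will be continued through Day 28". Discharge does not end it. Footnote + of A10.7 confirms that dosing at home is expected, because it plans to ask participants who leave early about adherence.

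The same footnote fixes when the scheduled assessments are made: "Assessments indicated in the table above will be ascertained at discharge or 28 days, whichever comes first". Master protocol section 7.1.2 applies the same cut-off to the visit that records outcomes and safety. The chemistry panel, which includes acid-base status, "is strongly recommended to be measured at days 1,3,7,14, and at hospital discharge"; no later measurement is named.

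After discharge, footnote + says that "participants will be contacted intermittently post-discharge, and that contact will be recorded in the EDC". The only content it names is this: "For participants discharged prior to Day 28, this will include information about treatment adherence", with timing near day 30.

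On safety, A10.10 says: "The rate of SAEs (including DKA) will be monitored". A10.12 adds that serious DKA events are collected. Neither states a time window or a way of learning about events at home.

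The A10.7 table marks outcomes assessment and the WHO scale in the 90-day column, but footnote ++ to that column mentions vital status only. Readmission within 28 days is a secondary endpoint (4.2.2), while the 90-day contact in 7.1.3 says only: "May include recording of hospital readmissions".

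**The concern.** The discharge-or-day-28 cut-off suits the other active arms. Arm C treatment is recommended for at least 14 days or until discharge, whichever is earlier, and Arm E is a single infusion. Arm F uses essentially the same footnote with one sentence on adherence added, although its treatment can outlast the hospital stay by weeks. The plan then checks whether tablets were taken at home without naming a question about what happened to the participant.

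Safety is objective 3 of the master protocol, and DKA is the one SAE that the Arm F appendix names. Rates labelled as Arm F safety rates would be read as covering the 28-day course, while systematic ascertainment covers only the part before discharge. Because the trial is open label, a participant or site that knows an SGLT2 inhibitor is being taken may be more likely, or less likely, to report an event than one in the control group. Spontaneous reporting can therefore bias the comparison as well as lower both rates.

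**Working it through.** The plan gives no figure on this point, so there is nothing to reproduce. The check sets the passages side by side and then sizes the exposed period.

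**Does any passage define ascertainment between an early discharge and day 28?**

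- Footnote + of A10.7 and section 7.1.2: scheduled assessment is at discharge. No.
- Intermittent contacts after discharge: they occur and are recorded, but adherence is the only named content. Not defined.
- 90-day column of A10.7: the table marks outcomes assessment, footnote ++ names vital status only. The two conflict.
- Readmission: a 28-day endpoint in 4.2.2, with optional recording in 7.1.3. No mandatory collection is stated.
- A10.10 and A10.12: SAEs and serious DKA are in scope, without window or method. Not defined.
- DKA monitoring in A10.7 and A10.8.1: acid-base checks are described for the hospital stay. No.
- Organ support (Appendix 2): a participant discharged without mechanical ventilation is taken to be free of organ support to day 21. The endpoint that adds renal replacement is confined to the index hospitalization. Not ascertained, by definition.
- Death: 28-day and 90-day mortality are endpoints and vital status is recorded at day 90. Yes, for death only.
- SAP: the version supplied covers the P2Y12 comparison, so its readmission endpoint cannot be used for Arm F.

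**How much of the course is exposed?** Treatment length is 28 days (A10.5). The discharge day d is an assumption; the only related statement is an expected stay of more than 72 hours (5.1). The share after discharge is (28 − d)/28.

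| Assumed discharge day | Days after discharge | Share of course |
|---|---|---|
| 5 | 23 | 82% |
| 7 | 21 | 75% |
| 10 | 18 | 64% |
| 14 | 14 | 50% |
| 21 | 7 | 25% |
| 28 | 0 | 0% |

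Arm F enrols moderate and severe participants, so the share for the whole arm depends on the mix. Assume mean stays of 7 days (moderate) and 21 days (severe), with a proportion p severe. The mean stay is 7(1 − p) + 21p. With p = 0 the share is 75%. With p = 0.25 the mean stay is 10.5 days and the share is 17.5/28 = 62.5%. With p = 0.5 it is 14/28 = 50%, and with p = 1 it is 7/28 = 25%.

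**How sensitive is the DKA comparison?** The earlier dapagliflozin trial cited in A10.1 had 2 DKA cases on drug and 0 on placebo among 1250 randomized. Assuming equal allocation, 2/625 = 0.32% of treated patients. If treatment had no effect, the chance that both cases fall on drug is (625/1250) × (624/1249) = 0.25, so the two-sided Fisher p is about 0.50. That is weak evidence of a difference. It does show that counts may be so small that one or two unreported cases would change the table the DSMB sees.

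**The case against.** The strongest reply is that follow-up plainly continues after discharge. Mortality is an endpoint at 28 and 90 days, contacts are made and recorded, the 90-day column marks outcomes assessment, participation lasts 90 days (5.5), and A10.10 and A10.12 set no cut-off at discharge. Footnote + says the contacts include adherence, which does not exclude other questions. Sections 7.3 and 7.4 refer to a platform adverse-event policy and a monitoring plan that were not supplied, and the manual of operations and case report form may add detail.

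All of this stands, and it rules out several stronger readings.

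- A reader might infer that outcome and safety assessment stops at discharge. It does not; what is missing is a defined method for non-fatal events.
- A reader might infer that most of the treated period goes unassessed. That holds only for discharge before day 14, and no length of stay is given.
- A reader might infer that the arm aims at 28-day organ protection and so cannot answer its question. A10.8.2 names death and organ support-free days, and the primary endpoint runs 21 days.
- A reader might infer that missed cases would erase an established DKA signal. Two cases against none is not one. Both were described as non-severe, their timing relative to discharge is not given, and A10.8.1 rates DKA as rare in type 2 diabetes (at least 1 in 10,000 but under 1 in 1,000).
- A reader might infer that the primary endpoint is wrong. Treating discharged participants as free of organ support is a deliberate platform-wide convention in Appendix 2.

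The reply does not supply the missing procedure. Unspecified content in a contact is not planned collection, and an open-ended duty to report does not ensure that a site hears of an event.

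**Conclusion.** The point holds as a gap in ascertainment. For Arm F participants discharged before day 28, the documents supplied name only adherence for the rest of the treatment course. They define no ascertainment of DKA, other SAEs or readmission, and two pairs of passages do not agree: the 90-day outcomes mark with footnote ++, and the 28-day readmission endpoint with its optional recording.

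The gap exists for any discharge before day 28. Its extent is 75%, 50% or 25% of the course for discharge on day 7, 14 or 21. These figures rest on assumed discharge days, and the share for the arm as a whole cannot be derived from the documents. The primary analysis of organ support-free days is unaffected. What is weakened is the safety comparison in A10.10 and the 28-day readmission endpoint. The conclusion assumes that the platform policy, monitoring plan, manual of operations and case report form do not already specify this content; if they do, the remedy is to cite it in Appendix 10.

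**What to change.** - In A10.7, make the existing contact near day 30 an outcome and safety contact as well. Ask the same questions in both arms: DKA, other SAEs, readmission, and any organ support or renal replacement since discharge, with event dates through day 28.
- In A10.10, state that SAE and DKA rates cover randomization to day 28 irrespective of discharge.
- Reconcile the 90-day outcomes assessment mark with footnote ++, and state where the 28-day readmission endpoint is collected.
- Leave the platform definition of organ support-free days as it is. Use organ support found after discharge only in a sensitivity analysis for Arm F, because changing the definition for one arm would break the common endpoint on which the platform model relies.

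The cost is a few more questions at a contact already planned, together with appendix and case report form wording. Event counts may rise slightly. No dose, treatment duration or clinical rule changes.

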### 3. Introduction

This is the statistical plan for the analysis of the ACTIV4A antiplatelet treatment trial. This plan has been pre-specified by the investigators prior to unblinding of the data.

#### 3.1. Reporting strategy

This SAP describes the planned analyses for the study. As outlined below, two cohorts (moderate illness, severe illness) may report at different times. Multiple reports describing the results of analysis may be prepared and published to ensure expedited dissemination of the study findings. It is anticipated that for each cohort, expedited, potentially preliminary reports will describe key primary and secondary findings and limited subgroup analyses.

Endpoints to be reported in these reports include:

- Organ support-free days to day 21 (primary endpoint)
- In-hospital mortality (key secondary endpoint)
- Major thrombotic events or death (key secondary endpoint)
- ISTH major bleeding (key safety endpoint)

Comprehensive reports providing complete characterization of trial results may subsequently be prepared and published.

### 4. Design Considerations

The study was designed with a Bayesian analysis as the primary analysis method for the trial. There is one overarching Bayesian model, pre-specified in the SAP, driving all adaptations, statistical triggers, and result summaries. The decision to use a Bayesian analysis was driven in part by the uncertainty of the extent of the pandemic. The required sample size could have been small or large. Given the expected evolution of the design and uncertain sample size, a Bayesian approach is more appropriate.

In this section we describe the basic defined structure of the analysis plan. This includes definitions for the patient subtypes, referred to as cohorts, the interventions, the primary endpoint, and the adaptive design.

#### 4.1. Patient Cohorts

There are two *illness states* defined for this analysis; the severe and moderate illness cohorts. The *severe illness state* is defined as a hospitalized patient on ICU-level organ-support at time of randomization. The *moderate illness state cohort* is defined as a hospitalized patient that is not in the severe illness state.

The primary analysis for the study creates two distinct populations to analyze potential differential benefit of the interventions. In this study these distinct groups are labeled as *cohorts*. The two cohorts are: 1) patients in the severe illness state; 2) patients in the moderate illness state at randomization.

#### 4.2. Interventions

The two interventions for this study are labeled as *antiplatelet agent* (P2Y12 inhibitor), which plays the inferential role of the investigational treatment and no antiplatelet agent

referred to as *control*, which plays the inferential role of the control arm. These interventions are defined as:

1. Antiplatelet agent (P2Y12 inhibitor) to achieve a high level of platelet inhibition in addition to usual care anticoagulation at a level recommended for the illness state.
2. No Antiplatelet agent: usual care strategies, including anticoagulation at a level recommended for the illness state.

#### 4.3. Primary Endpoint

The primary endpoint for the study is *organ support-free days* (OSFD). The endpoint is the number of days, out of the first 21 days after randomization, that a patient is alive and free of ICU-level organ support. For the purposes of the calculation of OSFDs, if a patient dies during their index hospitalization they will be considered the status of dead even if the death occurs after the first 21 days, through 90 days. If a patient dies during their acute index hospitalization they are coded as having  $-1$  OSFDs, which is the worst outcome for the measure. Any patient on ICU-level organ support for all of the first 21 days that does not die, will be labeled as  $0$  OSFDs, the second worst outcome. The number of days is rounded to the nearest day, creating an integer valued outcome. The values of  $0, 1, \dots, 21$  refer to the number of days alive and free of organ support, with smaller values being worse outcomes. Therefore, the primary outcome OSFDs is an ordinal outcome with 23 possible outcomes for each patient,  $-1, 0, 1, 2, \dots, 21$ . The details for the calculation of the endpoint is detailed in the data dictionary.

ICU-level of organ support is defined as high flow nasal cannula, non-invasive ventilation, invasive ventilation, extracorporeal life support, vasopressors, and/or inotropes delivered in an ICU or repurposed critical care area; high flow nasal cannula is considered to be organ support when applied inspiratory flow is  $\geq 20$  L/min and  $\text{FiO}_2 \geq 0.4$ . Due to the varying provision of organ-support in potentially repurposed areas during the pandemic, ACTIV-4a defines any hospitalized area able to deliver the above organ-support as an ICU. The details for the calculation of the endpoint is detailed in the data dictionary.

This primary endpoint is an ordinal outcome and the primary analysis model analyzes the outcome as ordinal, with a cumulative logistic proportional odds model. The details of the primary analysis model are presented in Section 12.1. The measure of relative efficacy for the interventions is an odds ratio (OR) which captures the effect of having improved outcomes in OSFDs across the scale between the two interventions. The model is structured so that for P2Y12 an  $\text{OR} > 1$  implies improved outcomes on OSFDs for the P2Y12 intervention compared to the control.

